2.4.1.2.5 Recurrent HF Hospitalizations at 24 Months

The power calculations for the recurrent HF hospitalizations at 24 months is based on the following assumptions:

- █ [Redacted]
- █ [Redacted]
- █ [Redacted]
- █ [Redacted]
- █ [Redacted]
- █ [Redacted]
- █ [Redacted]
- █ [Redacted]
- █ [Redacted]
- █ [Redacted]
- █ [Redacted]
- █ [Redacted]
- █ [Redacted]
- █ [Redacted]
- █ [Redacted]
- █ [Redacted]
- █ [Redacted]
- █ [Redacted]
- █ [Redacted]
- █ [Redacted]

Statistical Analysis Plan

Ten thousand (10,000) simulations were performed to calculate the sample size and power for this secondary endpoint. Based on the assumptions, with 450 randomized subjects, the power is approximately 80% to reject the null hypothesis at a one-sided 5% level of significance.

2.4.1.2.6 Freedom from All-Cause Mortality, Tricuspid Valve Surgery, and Tricuspid Valve Intervention at 24 Months

The power calculations for all-cause mortality or tricuspid valve surgery or intervention at 24 months is based on the following assumptions:

- [REDACTED]
- [REDACTED]
- [REDACTED]
- [REDACTED]
- [REDACTED]
- [REDACTED]
- [REDACTED]

Ten thousand (10,000) simulations were performed to calculate the sample size and power for this secondary endpoint. Based on the assumptions, with 450 randomized subjects, the power is approximately 80% to reject the null hypothesis at a two-sided 5% level of significance.

2.4.2 Single-Arm Cohort

2.4.2.1 Single-Arm Cohort – Primary Endpoint

The power calculation for the proportion of survival subjects with at least 10-point improvement in KCCQ overall summary score at 12 months over baseline for the Single-Arm Cohort is based on the following assumptions:

- [REDACTED]
- [REDACTED]
- [REDACTED]
- [REDACTED]
- [REDACTED]

Statistical Analysis Plan

[REDACTED]

Based on the assumptions, with 100 subjects, the power is about 90% to reject the null hypothesis; and with 200 subjects the overall power is more than 95% at a one-sided 2.5% level of significance. The details of the group sequential design can be found in Section 2.5.2.

2.4.2.2 Single-arm Cohort – Secondary Endpoints

The secondary endpoints of the Single-arm cohort will be evaluated only if the primary endpoint of the Single-arm cohort is met. Hence, the following secondary endpoints are adequately powered ($\geq 80\%$) with a sample size of 100 at the interim analysis for primary endpoint.

2.4.2.2.1 TR Reduction by at least 1 Grade at 30-Day Follow-up

The power calculation for TR reduction by at least 1 grade at 30-day post procedure for the Single-Arm Cohort is based on the following assumptions:

[REDACTED]

Ten thousand (10,000) simulations were performed to calculate the sample size and power for this secondary endpoint. Based on the assumptions, with 100 subjects, the power is about 90% to reject the null hypothesis at a one-sided 2.5% level of significance.

Statistical Analysis Plan

2.4.2.2.2 Freedom from MAE Occurring after Procedure Attempt (Femoral Vein Puncture) at 30 Days

The power calculation for MAE occurring after procedure attempt (femoral vein puncture) at 30-day post

[REDACTED]

■ [REDACTED]

■ [REDACTED]

[REDACTED]

■ [REDACTED]

[REDACTED]

[REDACTED] to calculate the sample size and power for this secondary endpoint. Based on the assumptions, with 100 subjects, the power is > 95% to reject the null hypothesis against the performance goal of 80% at a one-sided 2.5% level of significance.

2.4.2.2.3 Change in 6MWT (Six Minute Walk Test) Distance at 12 Months over Baseline

The power calculation for the change in 6MWT distance at 12 months over baseline for the Single-Arm Cohort is based on the following assumptions:

■ [REDACTED]

[REDACTED]

■ [REDACTED]

[REDACTED]

■ [REDACTED]

[REDACTED]

■ [REDACTED]

Ten thousand (10,000) simulations were performed to calculate the sample size and power for this secondary endpoint. Based on the assumptions, with approximately 100 subjects, the power is above 90% to reject the null hypothesis at a one-sided 2.5% level of significance.

2.4.2.2.4 Recurrent HF Hospitalizations at 12 Months

The power calculations for recurrent HF hospitalizations at 12 months for the Single-Arm Cohort is based on the following assumptions:

■ [REDACTED]

[REDACTED]

■ [REDACTED]

Statistical Analysis Plan

[REDACTED]

Ten thousand (10,000) simulations were performed to calculate the sample size and power for this secondary endpoint. Based on the assumptions, with approximately 100 subjects, the power is approximately 83% to reject the null hypothesis at a one-sided 2.5% level of significance.

2.4.2.2.5 Freedom from All-Cause Mortality and Tricuspid Valve Surgery at 12 Months

The power calculations for freedom from all-cause mortality and tricuspid valve surgery at 12 months for the Single-Arm Cohort is based on the following assumptions:

[REDACTED]

Ten thousand (10,000) simulations were performed to calculate the sample size and power for this secondary endpoint. Based on the assumptions, with 100 subjects, the power is approximately 83% to reject the null hypothesis at a one-sided 2.5% level of significance.

[REDACTED]

Statistical Analysis Plan

| [REDACTED]

| [REDACTED]

[REDACTED]

2.5 Interim Analysis

2.5.1 Sample Size Re-estimation for Randomized Cohort

[REDACTED]

2.5.2 Group Sequential Design for Single-arm Cohort

[REDACTED]

Statistical Analysis Plan

2.6 Timing of Analysis

2.6.1 Randomized Cohort

The analysis of the primary endpoints and the following secondary endpoints will be assessed when the 350th subject completes 12 months follow-up if there is no sample size increment, or the last subject resulted by the sample size re-estimation reaches 12 months follow-up.

- TR reduction to moderate or less at 30-day post procedure
- Freedom from MAE at 30 days
- Change in KCCQ at 12 months over baseline
- Change in 6MWT distance at 12 months over baseline

The analysis of the following secondary endpoints for the Randomized cohort will be assessed when all randomized subjects complete 24 months follow up.

- Recurrent HF hospitalizations at 24 months
- Freedom from All-cause mortality, tricuspid valve surgery, and tricuspid valve intervention at 24 months

2.6.2 Single-arm Cohort

If the primary endpoint of the Single-arm cohort is met at the interim analysis, the secondary endpoints of the Single-arm cohort will be evaluated for the same cohort as the primary endpoint. The Single-arm cohort endpoints of all additional subjects enrolled after the first 100 will be summarized descriptively. If the primary endpoint is not met at the interim analysis, then it will be re-analyzed when all enrolled subjects in the Single-Arm cohort complete 12 months follow-up.

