## TRILUMINATE Pivotal CIP (Version F)

A group sequential design with one interim analysis will be performed. The primary endpoint will be evaluated once the first 100 subjects have completed 12-month follow-up. If the primary endpoint is successfully met at the interim analysis, the Single-arm cohort endpoints will be summarized descriptively for all additional subjects enrolled after the first 100. If unsuccessfully met, the primary endpoint will be re-analyzed when all enrolled subjects in the Single-arm cohort have completed 12 months follow-up.

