### **6.8 Number of Subjects**

Approximately 450 subjects will be enrolled in the clinical investigation and randomized 1:1 to either the Device Group or to the Control Group. Enrollment into the Randomized cohort will continue until (1) the sample size re-estimation results are received and (2) enrollment meets the re-estimated sample size. The Single-arm cohort will enroll up to 200 eligible subjects, with enrollment continuing until the Randomized cohort has completed enrollment. Up to 3 roll-in subjects will be permitted per implanter without prior experience with the TriClip™ device.

Study Document No: ABT-CIP-10249

Study Name: TRILUMINATE Pivotal

**CONFIDENTIAL:** May not be reproduced outside of Abbott without written permission from Document Control. This is a quality record which will be retained per the local retention policy.

No site may enroll more than 25% of the total subjects.

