2.3.2 Single-Arm Cohort

2.3.2.1 Single-Arm Cohort – Primary Endpoint

The primary endpoint of the Single-arm Cohort is survival at 12 months with a quality of life improvement (assessed using KCCQ overall score) of at least 10 points compared to baseline. This endpoint will be assessed as a proportion of subjects meeting the definition of the endpoint.

The null and alternative hypotheses are stated as:

H₀: $P(12M) \leq 30\%$ vs.

H₁: $P(12M) > 30\%$

where $P(12M)$ represents the proportion of subject survival at 12 months with a quality of life improvement (assessed using KCCQ overall score) of at least 10 points compared to baseline. [REDACTED]

[REDACTED]
[REDACTED]
[REDACTED]
[REDACTED] The primary analysis will be performed on the Attempted Procedure population and the null hypothesis will be rejected at a one-sided 2.5% level of significance.

The performance goal was set based on the following clinical assumptions:

- [REDACTED]
[REDACTED]

Statistical Analysis Plan

[REDACTED]

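### After interim success in the Single-arm cohort, the primary estimate comes from the first 100 subjects alone; an all-subject estimate should be reported beside it

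*SAP*

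**What the plan says.** The primary endpoint of the Single-arm cohort is 12-month survival with a KCCQ gain of at least 10 points, tested against a 30% performance goal (SAP 2.3.2.1). Protocol 5.2.1 states: "A group sequential design with one interim analysis will be performed". It then sets the interim sample: "The primary endpoint will be evaluated once the first 100 subjects have completed 12-month follow-up".

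The two documents agree on what follows a successful interim. In Protocol 5.2.1, "the Single-arm cohort endpoints will be summarized descriptively for all additional subjects enrolled after the first 100". SAP 2.6.2 says the same, "The Single-arm cohort endpoints of all additional subjects enrolled after the first 100 will be summarized descriptively", and adds that the secondary endpoints are evaluated on the cohort used for the primary endpoint. If the interim does not succeed, the primary endpoint is analyzed again on all enrolled Single-arm subjects after 12 months.

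Enrollment does not hang on the interim. Protocol 6.8 reads: "The Single-arm cohort will enroll up to 200 eligible subjects, with enrollment continuing until the Randomized cohort has completed enrollment".

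Three other places bear on the point:
- Protocol 5.2.3 reports its descriptive list for all enrolled Single-arm subjects. The list includes change in KCCQ, change in 6MWT and TR grade.
- Protocol 9.1.2 says the Single-arm analysis covers all treated subjects.
- SAP 2.3.2.1 puts the primary analysis on the Attempted Procedure population.

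Neither of the last two mentions a restriction to the first 100.

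**The concern.** Under this rule, a favorable early result decides which subjects supply the primary estimate: the first 100 if the interim succeeds, everyone if it does not. An observed proportion that is reported because it reached a threshold exceeds the true proportion on average.

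Precision is also given up. Up to 100 further subjects are treated and followed in either case, but after interim success they do not enter the primary estimate. The descriptive list in Protocol 5.2.3 does not close the gap. It has no primary responder proportion, 12-month freedom from death or tricuspid valve surgery, 30-day major adverse events, or comparison of hospitalizations before and after enrollment.

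What is at stake is the size and interval of the reported response rate in the cohort with the harder anatomies. The decision to reject the null is not at stake.

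**Working it through.** **Inputs from the documents.** Null rate 30% (SAP 2.3.2.1). Level: "the null hypothesis will be rejected at a one-sided 2.5% level of significance". Interim at 100 subjects (Protocol 5.2.1). Maximum 200 (Protocol 6.8). Stated power (SAP 2.4.2.1): about 90% at the interim size of 100. For the maximum size the same section says: "with 200 subjects the overall power is more than 95% at a one-sided 2.5% level of significance".

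**Assumptions.** The interim boundary (SAP 2.5.2) and the assumed true rate (SAP 2.4.2.1) are blacked out. I used two common boundaries and ignored drop-out:
- Pocock, nominal one-sided 0.0147: success at 41 or more of 100; exact P(X ≥ 41 | 30%) = 0.0125.
- O'Brien-Fleming, nominal one-sided 0.0026: success at 44 or more of 100; exact P(X ≥ 44 | 30%) = 0.0021.

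**Step 1: the plan's own power.** It cannot be reproduced directly, so I solved for the true rate that gives 90% power at n = 100. This is 46.9% (cut 41) or 49.9% (cut 44). With final cuts of 75 or 74 of 200 respectively, exact overall type I error is 2.2% or 2.1%, and overall power is 99.7% or above 99.9%. The stated pair of powers is therefore coherent, and the test keeps its level.

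**Step 2: excess of the first-100 estimate given success.** For X ~ Binomial(n, p) and cut r:

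E[X | X ≥ r] − np = r(1 − p) · P(X = r) / P(X ≥ r)

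With n = 100 the result is in percentage points. At p = 0.40:
- cut 41: 41 × 0.60 × 0.0792 / 0.457 = 4.3
- cut 44: 44 × 0.60 × 0.0576 / 0.237 = 6.4

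| True rate | Cut 41: P(success) | Cut 41: excess | Cut 44: P(success) | Cut 44: excess |
|---|---|---|---|---|
| Rate giving 90% interim power | 90% | 1.0 | 90% | 1.0 |
| 44% | 76% | 2.0 | 54% | 3.7 |
| 40% | 46% | 4.3 | 24% | 6.4 |

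With the cut at 40 (no adjustment) or 45 (O'Brien-Fleming-type spending), the excess at 90% interim power is still about 1.0 point; at a true rate of 40% it is 3.6 and 7.2. Averaged over success and failure at the interim, the bias of the reported estimate is at most about 1.0 point.

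**Step 3: adding the later subjects.** If m later subjects have the same true rate and are not selected on the interim, the excess given success is multiplied by 100/(100 + m). With m = 100 it halves: 4.3 becomes 2.1 and 6.4 becomes 3.2. With m = 50 it falls by a third, to 2.8 and 4.3.

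**Step 4: precision.** Half-width = 1.96 × √(p(1 − p)/n). At p = 0.46:
- n = 100: 1.96 × √(0.2484/100) = 9.8 points
- n = 200: 1.96 × √(0.2484/200) = 6.9 points

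The ratio is 1/√2, so the interval is about 29% narrower if 200 enroll, whatever the true rate.

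**The case against.** Testing at the first boundary crossing and reporting the result is ordinary group sequential practice, and both documents prespecify it in the same way. At the effect the cohort is powered for, an excess of about 1 point is small beside a half-width of 9.8. The larger figures need a true rate near 40%, where the interim succeeds only 24% to 46% of the time. All of this stands.

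The later subjects' summary is not selected on the interim. It is therefore an independent check on the first-100 figure, and a reader could add the two sets for a simple proportion. The pooled figure, given success, still carries half the excess if 200 enroll. This also stands, and it is why both results should be shown. It does not remove the case for pooling, because the plan commits to no combined estimate or interval.

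Pooling assumes that early and later subjects share a response rate. Protocol 3.2.1 brings in a newer device generation, and SAP 2.8.3 summarizes the generations separately, so this may not hold. Enrollment may also stop short of 200.

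A reader might infer more than the documents support:
- That up to half the cohort goes unused. SAP 2.6.2 summarizes the endpoints of the later subjects, and Protocol 5.2.3 includes them in the descriptive list. They are outside the test and its estimate only.
- That no pooled or adjusted estimate exists. SAP 2.5.2, Protocol 9.4 and parts of SAP 2.3.2.1 are blacked out, so this cannot be shown.
- That the labeling claims are inflated by these amounts. SAP 2.11.2 ties those claims to the secondary endpoints. The calculation concerns the primary endpoint, and secondary endpoints are affected only as far as they correlate with it.

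**Conclusion.** This is a gap in estimation and reporting, minor in weight and cheap to close. After interim success the readable plan gives the primary response rate from the first 100 subjects and describes the rest apart. That estimate is then too high by about 1 point at the rate giving 90% interim power, 2 to 4 points at a true rate of 44%, and 4 to 6 points at 40%. These sizes rest on assumed cut-offs of 41 or 44 of 100 and no drop-out. The precision gain, from 9.8 to 6.9 points, rests on 200 enrolling and a common response rate.

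Type I error is not inflated, and trial success depends on the Randomized cohort alone (SAP 2.7). It would also go too far to say that the all-subject figure must replace the first-100 figure as the headline: that is a matter of preference. Reporting the two side by side is the part the documents support. Protocol 9.1.2, read literally, already points toward an analysis of all treated subjects and does not sit easily with SAP 2.6.2.

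**What to change.** Keep the interim test on the first 100 as the decision. Add to SAP 2.6.2 that, whatever the interim result, the primary endpoint and the five secondary endpoints are also estimated with 95% CI on all attempted Single-arm subjects once they complete the relevant follow-up, and that these estimates are reported beside the first-100 results. Because enrollment does not depend on the interim, an estimate reported in every case is free of the selection effect overall. Showing the first 100 and the later subjects separately as well lets a reader see whether they differ.

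Reconcile Protocol 9.1.2 with Protocol 5.2.1 and SAP 2.6.2, stating which analyses use the first 100 and which use all subjects. If SAP 2.5.2 already provides a pooled or adjusted estimate, a cross-reference from 2.6.2 is enough.

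The cost is one more set of tables on data already being collected. The all-subject figure arrives later than the interim and may be slightly less favorable.

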2.7 Study/Trial Success

Trial success will be declared when the primary endpoint for the Randomized cohort is met.

2.8 Subgroups for Analysis

2.8.1 Subgroups for Analysis for the Randomized Cohort

2.8.1.1 Sex (Male vs. Female)

Subgroup analyses of sex will be performed for analysis of the primary endpoint components in the Randomized Cohort. Major baseline and clinical characteristics will be summarized by treatment groups and sex.

Statistical Analysis Plan

[REDACTED]

[REDACTED]

2.8.1.2 Baseline TR Grading (Grade 3 vs. > Grade 3)

Subgroup analyses of baseline TR grading will be performed for the analysis of the primary endpoint components in the Randomized Cohort. Major baseline and clinical characteristics will be summarized by treatment group and TR grading at baseline.

[REDACTED]

2.8.1.3 Baseline NYHA Functional Class (I/II vs. III/IV)

Subgroup analyses of the baseline NYHA functional class (I/II vs. III/IV) will be performed for analysis of the primary endpoint components in the Randomized Cohort. Major baseline and clinical characteristics will be summarized by treatment groups and device type.

[REDACTED]

Statistical Analysis Plan

[REDACTED]

2.8.1.4 Baseline Etiology of TR (Primary TR vs. Secondary TR)

If there were at least 10% of subjects in each of the subgroups, the subgroup analyses of baseline etiology of TR (primary TR vs. secondary TR) will be performed for analysis of the primary endpoint components for the Randomized Cohort. Major baseline and clinical characteristics will be summarized by treatment group and baseline etiology of TR.

[REDACTED]

2.8.2 **Subgroups for Analysis for the Single-arm Cohort**

2.8.2.1 Sex (Male vs. Female)

Subgroup analyses of sex will be performed for analysis of the primary endpoint for the Single-Arm Cohort. Major baseline and clinical characteristics will be summarized by sex.

[REDACTED]

Statistical Analysis Plan

2.8.2.2 Baseline TR Grading (\leq Grade 4 vs. Grade 5)

If there were at least 20 subjects in each of the subgroups, the subgroup analyses of baseline TR grading will be performed for analysis of the primary endpoint for the Single-Arm Cohort. Major baseline and clinical characteristics will be summarized by baseline TR grading subgroup.

[REDACTED]

2.8.2.3 Baseline NYHA Functional Class (I/II vs. III/IV)

Subgroup analyses of baseline NYHA functional class (I/II vs. III/IV) will be performed for analysis of the primary endpoint for the Single-Arm Cohort. Major baseline and clinical characteristics will be summarized by device type.

[REDACTED]

2.8.2.4 Baseline Etiology of TR (Primary TR vs. Secondary TR)

Subgroup analyses of baseline etiology of TR will be performed for analysis of the primary endpoint for the Single-Arm Cohort. Major baseline and clinical characteristics will be summarized for each subgroup at baseline.

[REDACTED]

2.8.3 **Subgroup Analysis for TriClip™ System vs. TriClip™ G4 System**

Subgroup analyses for TriClip™ system vs. TriClip™ G4 system will be performed. Subjects in the Randomized Device group and Single-Arm cohort who have the TriClip™ index procedure attempted with the TriClip™ system will be included in the TriClip™ system subgroup, while subjects in the Randomized Device group and Single-Arm cohort who have the TriClip index procedure attempted with the TriClip™ G4 system will be included in the TriClip™ G4 system subgroup. Baseline and echocardiographic characteristics, procedure outcome and TR grading over time will be summarized descriptively in these two subgroups.

Statistical Analysis Plan

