**TRILUMINATE Pivotal CIP**  
(Version F)

	
In addition, up to 200 subjects will be enrolled into a concurrent Single-arm cohort. This cohort will comprise subjects with tricuspid valve anatomies, where:
 
 
• The likelihood of achieving TR reduction to moderate or less is low, and
 
• The likelihood of achieving TR reduction of at least 1 grade (as assessed using a 5-grade scale) is high
 
 
Determination of enrollment into the Single-arm cohort will be made by an independent eligibility committee.
 
An imaging sub-study (comprised of Cardiac magnetic resonance imaging, computed tomography and/or real-time echo) of approximately 100 subjects will be conducted to evaluate quantitative parameters associated with TR reduction.

Key Inclusion Criteria	
 
• In the judgment of the sites local heart team, subject has been adequately treated per applicable standards (including medical management) and stable for at least 30 days. The patient must be optimally treated, and confirmed with the EC: 
 
• Medical therapy for TR
 
• Medical and/or device therapy, for mitral regurgitation, atrial fibrillation, coronary artery disease and heart failure
 
 
 
• Subject is symptomatic with Severe TR despite being optimally treated, as described above. TR severity is determined by the assessment of a qualifying transthoracic echocardiogram (TTE) confirmed by the Echocardiography Core Lab (ECL). The ECL will also request a transesophageal echocardiogram (TEE) to confirm TR etiology. Note: If any cardiac procedure(s) occur after eligibility was determined and prior to TriClip™ procedure, TR severity 30-day after the cardiac procedure(s) will be reassessed
 
• The cardiac surgeon of the site local heart team (consisting of one interventionalist, one cardiac surgeon, one heart failure specialist and one echocardiologist) concur that the patient is at intermediate or greater estimated risk for mortality or morbidity with tricuspid valve surgery.
 
• New York Heart Association (NYHA) Functional Class II, III or ambulatory IV
 

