**TRILUMINATE Pivotal CIP**  
(Version F)

	
 
• Cardiac Output
 
• Forward Stroke Volume (Left Ventricle)
 
• Inferior Vena Cava Dimension
 
• Same endpoints as assessed with echocardiography to be obtained from MRI/CT in the subset of patients participating in the imaging sub-study at baseline, 30 days and 12 months
 

Sample Size / Targeted Number of Subjects to Receive Study Device
	
Approximately 450 subjects will be randomized in a 1:1 ratio at up to 80 sites, out of which approximately 225 are expected to receive the TriClip™ device. Up to 200 additional subjects will be enrolled into a concurrent Single-arm cohort, all of whom will receive the TriClip™ device.
 
Up to 3 roll-in subjects per implanter may be enrolled at sites with operators who do not have prior or recent experience using the TriClip™ device.

Subject Follow-up
	
Upon randomization, subjects will be scheduled for a “Treatment” visit. At the “Treatment” visit, Device group subjects will undergo the TriClip™ procedure and Control group subjects will be seen by a Heart Failure specialist for a physical exam, including vital signs, cardiac health status and evaluation of heart failure medications. The Treatment visit must be completed within 14 days of randomization.
 
Subjects will have required follow-up evaluations at these time points post- “Treatment” visit: Discharge (not applicable to control subjects), 30 days, 6 months, 12 months, 18 months and annually thereafter through 5 years.

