**TRILUMINATE Pivotal CIP**  
(Version F)

TriClip XT Clip Delivery Sys CLIN	TCDS0203-XT	Serialized	Abbott	USA/Cana da	Investigational
TriClip XT Delivery Sys	TCDS0202-XT	Serialized	Abbott	EU	Market Released

The newest generation TriClip™ device (TriClip™ G4) will also be included in the trial. Further information regarding the TriClip™ G4 device can be found in the Instructions for Use (IFU) for the respective region (see below). Sites in the EU may use the TriClip™ G4 device only after it is CE marked and commercially available for participating study sites (using the commercial product).

Device Name	Model/Type	Serial/Lot Controlled	Manufacturer	Region/Country	Investigational or Market Released
TriClip Steerable Guide Cath CLIN	TSGC0203	Serialized	Abbott	USA/Cana da	Investigational
TriClip Steerable Guide Cath CE	TSGC0202	Serialized	Abbott	European Union (EU)	Market Released
TriClip G4 NT Clip Delivery Sys CLIN	TCDS0303-NT	Serialized	Abbott	USA/Cana da	Investigational
TriClip G4 NT Delivery Sys CE	TCDS0302-NT	Serialized	Abbott	EU	Market Released
TriClip G4 XT Clip Delivery Sys CLIN	TCDS0303-XT	Serialized	Abbott	USA/Cana da	Investigational
TriClip G4 XT Delivery Sys CE	TCDS0302-XT	Serialized	Abbott	EU	Market Released
TriClip G4 NTW Clip Delivery Sys CLIN	TCDS0303-NTW	Serialized	Abbott	USA/Cana da	Investigational
TriClip G4 NTW Delivery Sys CE	TCDS0302-NTW	Serialized	Abbott	EU	Market Released
TriClip G4 XTW Clip Delivery Sys CLIN	TCDS0303-XTW	Serialized	Abbott	USA/Cana da	Investigational

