1.3 Clinical Investigation Design

TRILUMINATE Pivotal trial is a prospective, multicenter, randomized, controlled, clinical trial of the TriClip™ device in symptomatic subjects with severe TR, who have been determined by the site's local heart team to be at intermediate or greater estimated risk of mortality or morbidity with tricuspid valve surgery.

The trial consists of two cohorts: Randomized cohort and Single-arm cohort. Determination as to whether a patient is placed in the Randomized cohort or Single-arm cohort will be made by the independent eligibility committee. Patients will be placed in the Single-arm cohort if they meet the following criteria:

- The likelihood of achieving TR reduction of at least 1 grade (as assessed using a 5-grade scale) is high, and
- The likelihood of achieving TR reduction to moderate or less (≤ 2) is low

All other patients will be randomized.

Randomization will occur in a minimum of 350 eligible subjects in a 1:1 ratio to receive either the TriClip™ device or medical therapy (control group), at up to 80 sites as follows:

- **TriClip™ Device (Device) Group:** Eligible subjects will undergo the TriClip procedure and will continue to be managed on medical therapy, per physician discretion.
- **Medical Therapy (Control) Group:** Eligible subjects will not undergo the TriClip procedure but will continue to be managed on medical therapy, per physician discretion.

The Single-arm cohort will enroll approximately 200 eligible subjects and all subjects will receive the TriClip™ device.

Statistical Analysis Plan

Additionally, up to 3 roll-in subjects will be permitted per implanter without prior experience of transcatheter treatment of the tricuspid valve. The trial will be conducted in US, Canada and Europe, with a minimum of 50% of the subjects in each cohort enrolled in the US.

Following the completion of enrollment of the TRILUMINATE Pivotal trial, subjects from eligible sites will be enrolled into a continued access study (CAS). Details of the analysis plan to continued access study is included in Appendix B.

An independent Clinical Events Committee (CEC) will adjudicate events including cause of death, HF hospitalization and components of major adverse events. The independent ECL will assess echocardiographic endpoints.

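### SAP 2.8.3 pools two cohorts with different expected TR results in its TriClip versus TriClip G4 summary, so cohort mix can imitate or hide a difference in achieved TR grade

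*SAP*

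**What the plan says.** SAP 2.8.3 defines its first subgroup as "Subjects in the Randomized Device group and Single-Arm cohort who have the TriClip™ index procedure attempted with the TriClip™ system"; the G4 subgroup is formed in the same way. For both it says: "Baseline and echocardiographic characteristics, procedure outcome and TR grading over time will be summarized descriptively in these two subgroups". Nothing in that section is blacked out, and it contains no split, weighting or adjustment by cohort.

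The Design entry of the Protocol Summary gives two conditions for the Single-arm cohort. One concerns the grade that can be reached: "The likelihood of achieving TR reduction to moderate or less is low, and". The other, which points in the opposite direction, concerns the size of the improvement: "The likelihood of achieving TR reduction of at least 1 grade (as assessed using a 5-grade scale) is high". The eligibility committee makes the decision. SAP 1.3 adds: "All other patients will be randomized".

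On device generation, protocol 3.2.1 says: "The newest generation TriClip™ device (TriClip™ G4) will also be included in the trial". EU sites may use G4 only once it is CE marked and commercially available to them. No section assigns generation by chance or fixes the cohort ratio within a generation.

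On size, the Protocol Summary plans about 450 randomized subjects, "out of which approximately 225 are expected to receive the TriClip™ device", and says: "Up to 200 additional subjects will be enrolled into a concurrent Single-arm cohort".

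**The concern.** The cohorts are sorted on a forecast of the result that SAP 2.8.3 then tabulates. A Single-arm subject is one in whom TR is not expected to reach moderate or less, so achieved TR grade should be worse there whichever generation is used. Elsewhere the SAP keeps the cohorts apart: 2.11 evaluates their endpoints separately, and the 30-day freedom-from-MAE goals differ (90% in 2.3.1.2.2, 80% in 2.3.2.2.2). Section 2.8.3 merges them without giving a reason.

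G4 was added as a newer generation, so its use follows supply, region and calendar time. If the proportion of Single-arm subjects also differs between the generations, a pooled TR table mixes device performance with patient selection and can err in either direction.

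What is at stake is interpretation. This is the only comparison of the generations in the readable text, and SAP Appendix B says that every Continued Access subject receives G4. Readers are therefore likely to look to this table when they ask whether first-generation results apply to G4.

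**Working it through.** SAP 2.8.3 states no rate, sample size or error level, so there is no planned figure to reproduce. The check is mixture arithmetic with device performance held identical across generations.

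**Inputs**
- Randomized Device group: about 225. Single-arm cohort: up to 200 (Protocol Summary; SAP 1.3 says approximately 200). The Randomized share of the pool is 225/425 = 52.9%.
- TR moderate or less at 30 days in the Randomized Device group: 70% (SAP 2.4.1.2.1, a planning assumption).
- The same rate in the Single-arm cohort, *s*: no figure is readable, only that the likelihood is low. Assumed 20%, 30% or 40%.
- Randomized share within each generation, *a*: not given. Assumed.

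**Formulas**
- Pooled rate = 0.70·*a* + *s*·(1 − *a*).
- Spurious gap, G4 minus TriClip = (*a*_G4 − *a*_TriClip)·(0.70 − *s*).
- Constraint: the two shares average to 52.9%, weighted by subgroup size, so they must lie on either side of it (or both equal it).

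**Are the example shares possible at 225 + 200?** The fraction of subjects treated with TriClip is (0.529 − *a*_G4)/(*a*_TriClip − *a*_G4).
- 60% and 45%: 0.0794/0.15 = 0.529, about 225 TriClip and 200 G4 subjects. Possible.
- 70% and 40%: 0.1294/0.30 = 0.431, about 183 TriClip and 242 G4 subjects. Possible.

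**Results with no true generation effect**

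| Randomized share, TriClip / G4 | *s* | Pooled TriClip | Pooled G4 | Spurious gap (points) |
|---|---|---|---|---|
| 60% / 45% | 20% | 50.0% | 42.5% | −7.5 |
| 60% / 45% | 30% | 54.0% | 48.0% | −6.0 |
| 60% / 45% | 40% | 58.0% | 53.5% | −4.5 |
| 70% / 40% | 20% | 55.0% | 40.0% | −15 |
| 70% / 40% | 30% | 58.0% | 46.0% | −12 |
| 70% / 40% | 40% | 61.0% | 52.0% | −9 |
| equal | any | same | same | 0 |

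Swapping the shares between generations reverses the sign. Widening *s* to 10% to 50% widens the ranges to 3 to 9 points (0.15 × 0.20 to 0.15 × 0.60) and 6 to 18 points (0.30 × 0.20 to 0.30 × 0.60).

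**Masking.** Suppose G4 truly adds 10 points in both cohorts, *s* is 30% with TriClip, and the Randomized shares are 70% and 40%. TriClip shows 0.70 × 0.70 + 0.30 × 0.30 = 58%. G4 shows 0.40 × 0.80 + 0.60 × 0.40 = 56%. A 10-point gain appears as a 2-point loss.

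**Within cohort.** When the summaries are separate, or standardized to one cohort mix, the spurious gap is 0 by construction.

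**The case against.** The case on the other side is substantial, and much of it stands.

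- **Nothing formal depends on the table.** It has no hypothesis or error level. Trial success rests on the Randomized primary endpoint (SAP 2.7) and labeling claims on the listed secondary endpoints (SAP 2.11). A reader might infer a threat to the trial's conclusions; the documents do not support that.
- **The bias needs unequal shares.** The cohorts enroll concurrently, the Single-arm cohort stays open until the Randomized cohort completes enrollment (protocol 6.8), and at least half of each must be enrolled in the US. G4 use that tracks time or region does not by itself change the cohort ratio. A reader might infer that G4 will look worse; neither the existence nor the direction of an imbalance is documented.
- **Shares cannot be chosen freely.** At 225 + 200, Randomized shares of 70% and 60% are impossible because both exceed 52.9%. Shares of 80% and 50% would leave only about 10% of subjects, some 42 of 425, in the TriClip subgroup. The examples above respect this limit.
- **The selection has two sides.** Single-arm subjects must also be likely to improve by at least 1 grade. Device Success uses that criterion and Procedural Success builds on it (protocol 5.1.3 and 5.2.3). A reader might infer a built-in deficit on every procedural outcome; none is shown for these two. SAP 2.8.3 also does not name the proportion at moderate or less; it is one cut of the TR grading that the section does list.
- **Partial safeguards exist.** Baseline summaries in the same subgroups may expose an imbalance in TR severity. SAP 2.8.1.3 and 2.8.2.3 mention baseline summaries by device type within cohort, possibly a drafting slip. SAP 3.5 reports descriptive endpoints by cohort, but not by generation. None of these corrects the pooled outcome table.
- **Redaction.** The specific poolability text in SAP 2.10.1 and 2.10.2 and part of protocol 9.5 are blacked out, so a related check cannot be excluded. SAP 2.8.3 does not refer to one.
- **Purpose.** SAP 2.8.3 does not say that it is meant to carry results over to G4. That use is likely, but it is an inference.

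**Conclusion.** The concern holds in a limited form. As written, the pooled summary of achieved TR grade cannot separate device generation from cohort mix. At the planned sizes, a 15-point difference in Randomized share produces a spurious gap of 4.5 to 7.5 points, and a 30-point difference 9 to 15 points; with equal shares there is no gap. These sizes rest on the SAP's 70% planning rate and on assumed Single-arm rates and cohort shares. They show what the layout allows and do not predict what will occur. The consequence is possible misreading of a descriptive table, so this is an inexpensive improvement to the SAP and not a defect in the trial's inference.

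**What to change.** In SAP 2.8.3, present the TriClip and TriClip G4 summaries separately within the Randomized Device group and the Single-arm cohort, each with baseline TR grade, and state the cohort share in each generation. If an overall figure is wanted, standardize both generations to a common cohort mix. The unweighted pooled figure can stay if labelled secondary; it need not be removed.

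The cost is SAP wording only, because cohort and index device already define the subgroups. The downside is smaller cells. Splitting by cohort does not remove confounding by calendar time or region, and a note to the table should say so.
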